There thus remains a significant unmet medical need for the investigation and development of novel IPF treatments targeting disease-relevant pathways. Several other candidate treatments with different mechanism of action are currently in Phase II and III or in earlier phases of clinical development. Considering the progressive and irreversible nature of this disease, it is highly desirable to evaluate efficacy of new potential treatments when added on top of the local standard of care.

Over the last decade, a growing number of G protein-coupled receptors (GPCRs) have been identified for which the ligands are energy substrates or metabolic intermediates. Free fatty acids (FFAs) have been reported to activate different GPCRs, including FFA1, FFA2, FFA3, FFA4, and GPR84. These FFA-sensing receptors are proposed to play important roles in the pathophysiology of a variety of diseases, including neuro-inflammatory diseases and metabolic disorders. GPR84 has been described as a pro-inflammatory receptor. The ligand-induced activation of GPR84 mediates both activation and migration of neutrophils and

macrophages, which play crucial roles in the maintenance of homeostasis in several clinical pathologies such as neuro-inflammation, metabolic disorders, chronic pain and fibrotic diseases like pulmonary fibrosis.

Moreover, nonclinical effects with GLPG1205, a GPR84 antagonist, in disease-relevant models suggest an important role for the receptor in the pathogenesis of pulmonary fibrosis.

GPR84 has been described to play an important role in fibrotic processes, which is demonstrated with GPR84 knock-out mice that displayed significantly reduced kidney fibrosis compared to wild type mice in a chronic kidney model induced with adenine-supplemented diet [20]. In addition, PBI-4050 a compound in clinical development targeting GPR84 as well as GPR40, has shown benefit in patients with IPF with and without addition of nintedanib [21].

GLPG1205 is a novel, potent and selective inhibitor of GPR84, and the first of its class in clinical development for the oral treatment of pulmonary fibrosis. In the following, a summary of the nonclinical and clinical development of GLPG1205 is presented. For full details, the reader is referred to the most current version of the investigator brochure (IB) and any relevant addenda.

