Appendix 4 Normal Ranges

NORMAL RANGES FOR VITAL SIGNS

Normal ranges applicable in supine position (after 5 minutes):

Systolic blood pressure (mmHg)	Diastolic blood pressure (mmHg)	Heart rate (bpm)	Oral/Tympanic temperature (°C)	Respiratory rate (RR) (breaths/minute)
$90 \leq \text{SBP} \leq 150$	$45 \leq \text{DBP} \leq 90$	$50 \leq \text{HR} \leq 100$	$35.5 \leq t^{\circ} \leq 37.5$	$12 \leq \text{RR} \leq 18$

NORMAL RANGES FOR ECG PARAMETERS

Normal ranges applicable in supine position (after 5 minutes):

PR (ms)	QRS (ms)	QTcF (ms)	Heart rate (bpm)
$120 \leq \text{PR} \leq 220$	$\text{QRS} \leq 120$	QTcF ≤ 450 (male) QTcF ≤ 460 (female)	$50 \leq \text{HR} \leq 100$

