5.3.2.3. Definition of Toxicity Grades

Toxicity grades will only be derived for laboratory tests specified in this section. For other tests, only the classification according to normal ranges will be used (Section 5.3.2.4).

Toxicity grades will be determined as implemented in the attached table (appendix) based on CTCAE, v5.0: November 27, 2017.

Note: when no explicit grade (e.g. “G1”) is included, the categories will be labeled as indicated by the thresholds.

In addition, the following criteria will be used:

Table 5 Additional Toxicity Grading

Tests	Thresholds (Conventional Units)	Thresholds (SI Units)
Hematology		
Eosinophiles relative count	>5%	>5%
Coagulation		
Prothrombin time (PT)	>ULN - 1.5 x ULN >1.5 - 2.5 x ULN >2.5 x ULN	>ULN - 1.5 x ULN >1.5 - 2.5 x ULN >2.5 x ULN
Chemistry		
Random glucose increased (fasting)	>130 mg/dl	> 7.2 mmol/L
High density lipoprotein (HDL)	<60 mg/dL	<1.554 mmol/L
Low density lipoprotein (LDL)	>160 mg/dL	>4.144 mmol/L

To investigate elevated liver function, the following additional grading (based on the exclusion and discontinuation criteria in the CSP) is defined.

Table 6 Additional Toxicity Grading for Liver Function

Tests	Thresholds
AST	AST >1.5 - <=3 x ULN AST >3 - <=5 x ULN AST >5 - <=8 x ULN AST >8 x ULN
ALT	ALT >1.5- <=3 x ULN ALT >3 - <=5 x ULN ALT >5 - <=8 x ULN ALT >8 x ULN

Tests	Thresholds
AST / ALT combination	ALT and/or AST >1.5 - <=3 x ULN AST and /or ALT >3 - <=5 x ULN AST and /or ALT >5 - <=8 x ULN AST and /or ALT >8 x ULN
AST / ALT / total bilirubin combination	Bilirubin >2 x ULN AND AST or ALT >3 x ULN
AST / ALT / INR combination	INR >1.5 AND AST or ALT >3 x ULN
AST / ALT / eosinophiles relative count combination	Eosinophils >5% AND AST or ALT >3 x ULN

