5.3.2.4. Definition of Non-Graded Abnormalities

For laboratory tests provided by the laboratory, the position of the actual analysis values versus their normal ranges will be determined directly by using the position indicator provided in the database as reported by the central laboratory, expressing the classes for these analysis values as low (L), normal (N) or high (H). L, N, and H are further referred to as non-graded abnormalities.

Only for tests for which no toxicity gradings are specified in Section 5.3.2.3, analysis of the classification according to normal ranges will be done.

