5.3.3.3. Abnormalities

The actual analysis values and changes from baseline of the QT and QTcF parameters will be categorized into the abnormality classes as defined in ICH-E14 The Clinical Evaluation of QT/QTc Interval Prolongation and Proarrhythmic Potential for Non-Antiarrhythmic Drugs (Step 4 Version). For PR and HR the categorization as specified in the protocol is used.

Table 7 Abnormalities on ECG Parameters

Parameter	Abnormality	Limits
Abnormalities on actual values		
QT and QTcF (ms)	QT ≤ 450 450 < QT ≤ 480 480 < QT ≤ 500 QT > 500	≤ 450 450 < value ≤ 480 480 < value ≤ 500 > 500
PR (ms)	L N H	< 120 120 ≤ value ≤ 220 > 220
HR (bpm)	L N H	< 50 50 ≤ value ≤ 100 > 100
Abnormalities on change from baseline		

QT and QTcF (ms)	QT change \leq 30	\leq 30
	30 < QT change \leq 60	30 < change \leq 60
	QT change > 60	> 60

Worst-Case Abnormality

The worst-case post-baseline categorized actual analysis value and the worst-case categorized change from baseline will be determined per subject, per parameter, and for each analysis period, using all non-missing post-baseline records (including unscheduled and follow-up visits).

For QT and QTcF, the worst-case categorized actual analysis value is the category corresponding to the highest post-baseline actual value. The worst-case change from baseline is the category corresponding to the largest increase (positive change) from baseline.

For PR and HR, the worst-case post-baseline abnormality L, N or H is determined as follows:

- L = low: at least one post-baseline result is classified as L.
- N = normal: all post-baseline results are classified as N.
- H = high: at least one post-baseline result is classified as H.

If, for a subject, both L and H are reported, the subject will be counted twice in a table: once with a worst-case L and once with a worst-case H.

Treatment-Emergent Abnormalities

For QT and QTcF, an abnormal post-baseline category for actual values is defined as treatment-emergent when the abnormality is worse compared to the abnormality at baseline. When the baseline value is missing, post-baseline abnormalities are considered as treatment-emergent. An abnormal category for change from baseline is always treatment-emergent.

For PR and HR, post-baseline abnormalities L or H are defined as treatment-emergent when they differ from the abnormality class of the baseline result. When the baseline result is missing, post-baseline abnormalities L or H are considered as treatment-emergent.

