APPENDIX

APPENDIX I: LABORATORY: TOXICITY GRADING

Implementation of Common Terminology Criteria for Adverse Events (CTCAE), v5.0: November 27, 2017.

Notes:

- Laboratory results for which the fasting status is missing will be considered as taken non-fasted.
- Analysis results scoring below the lowest grade limits (< grade 1) are defined as grade 0.

Table 8 Laboratory Toxicity Grades based on CTCAE v5.0

Tests	Thresholds (Conventional Units)	Thresholds (SI Units)	Grade
Hematology			
Hemoglobin decreased	<LLN - 10 g/dL	<LLN - 100 g/L	G1
	<10 - 8 g/dL	<100 - 80 g/L	G2
	<8 g/dL	<80 g/L	G3
Hemoglobin increased	>ULN - ULN + 2 g/dL	>ULN - ULN + 20 g/L	G1
	>ULN + 2 - ULN + 4 g/dL	>ULN + 20 - ULN + 40 g/L	G2
	>ULN + 4 g/dL	>ULN + 40 g/L	G3
White blood cell (WBC) count decreased	<LLN - 3000 /mm ³	<LLN - 3.0 * 10 ⁹ /L	G1
	<3000 - 2000 /mm ³	<3.0 - 2.0 * 10 ⁹ /L	G2
	<2000 - 1000 /mm ³	<2.0 - 1.0 * 10 ⁹ /L	G3
	<1000 /mm ³	<1.0 * 10 ⁹ /L	G4
WBC count increased	>100000 /mm ³	>100.0 * 10 ⁹ /L	G3
Neutrophils decreased	<LLN - 1500 /mm ³	<LLN - 1.5 * 10 ⁹ /L	G1
	<1500 - 1000 /mm ³	<1.5 - 1.0 * 10 ⁹ /L	G2
	<1000 - 500 /mm ³	<1.0 - 0.5 * 10 ⁹ /L	G3
	<500 /mm ³	<0.5 * 10 ⁹ /L	G4
Lymphocytes decreased	<LLN - 800 /mm ³	<LLN - 0.800 * 10 ⁹ /L	G1
	<800 - 500 /mm ³	<0.8 - 0.5 * 10 ⁹ /L	G2
	<500 - 200 /mm ³	<0.5 - 0.2 * 10 ⁹ /L	G3
	<200 /mm ³	<0.2 * 10 ⁹ /L	G4
Lymphocytes increased	>4000 /mm ³	>4.0 * 10 ⁹ /L	G2
	>20000 /mm ³	>20.0 * 10 ⁹ /L	G3
Eosinophiles absolute count	>ULN	>ULN	G1
Platelets decreased	<LLN - 75000 /mm ³	<LLN - 75.0 * 10 ⁹ /L	G1
	<75000 - 50000 /mm ³	<75.0 - 50.0 * 10 ⁹ /L	G2
	<50000 - 25000 /mm ³	<50.0 - 25.0 * 10 ⁹ /L	G3
	<25000 /mm ³	<25.0 * 10 ⁹ /L	G4
Coagulation			
Activated partial thromboplastin time (aPTT)	>ULN - 1.5 x ULN	>ULN - 1.5 x ULN	G1
	>1.5 - 2.5 x ULN	>1.5 - 2.5 x ULN	G2
	>2.5 x ULN	>2.5 x ULN	G3
INR (international normalized ratio) increased	>1.2 - 1.5	>1.2 - 1.5	G1
	>1.5 - 2.5	>1.5 - 2.5	G2

	>2.5		>2.5		G3
Chemistry					
Random glucose decreased (fasting)	<LLN - 55	mg/dl	<LLN - 3.0	mmol/L	G1
	<55 - 40	mg/dl	<3.0 - 2.2	mmol/L	G2
	<40 - 30	mg/dl	<2.2 - 1.7	mmol/L	G3
	<30	mg/dl	<1.7	mmol/L	G4
Creatinine increased	>ULN - 1.5 x ULN		>ULN - 1.5 x ULN		G1
	>1.5 - 3x ULN		>1.5 - 3 x ULN		G2
	> 3 - 6 x ULN		> 3 - 6 x ULN		G3
	>6 x ULN		>6 x ULN		G4
eGFR (estimated glomerular filtration rate)/creatinine clearance ml/min/1.73 m ²	<LLN - 60	ml/min	<LLN - 60	ml/min	G1
	<60 - 30	ml/min	<60 - 30	ml/min	G2
	<30 - 15	ml/min	<30 - 15	ml/min	G3

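### SAP 5.3.2.4 leaves high absolute neutrophils, high platelets and WBC between the ULN and 100 x 10^9/L counted as grade 0 in the laboratory abnormality tables

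*SAP*

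**What the plan says.** SAP 5.3.2.3 brings in the appendix table: "Toxicity grades will be determined as implemented in the attached table (appendix) based on CTCAE, v5.0: November 27, 2017". SAP 5.3.2.4 takes each result's low, normal or high (L/N/H) position from the central laboratory's indicator, then limits its use: "Only for tests for which no toxicity gradings are specified in Section 5.3.2.3, analysis of the classification according to normal ranges will be done". Appendix I adds a default: "Analysis results scoring below the lowest grade limits (< grade 1) are defined as grade 0".

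In Table 8, neutrophils and platelets have rows for decreases only. The row "WBC count increased" has a single cut, grade 3 above 100,000/mm3 (100 x 10^9/L).

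Under SAP 5.3.2.6, a graded result is treatment-emergent only if it reaches grade 1 to 4 and exceeds the baseline grade. SAP 5.3.2.8 plans shift tables, a frequency table of treatment-emergent worst cases, and a listing of results that are both treatment-emergent and out of range. Graded and non-graded results are shown separately.

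SAP 5.3.2.2 plans normal-range tabulations for glucose and triglycerides, although both are graded.

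For ECG, SAP 5.3.3.3 says: "For PR and HR the categorization as specified in the protocol is used". QRS is among the parameters to be analysed (5.3.3.1), and protocol Appendix 4 gives it a normal range of up to 120 ms, but Table 7 has no QRS row.

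**The concern.** The rule treats a test as covered once any grading exists for it, even if that grading looks in one direction only or starts far beyond the normal limit. For three blood counts, a new high value is then tabulated in the same cell as a normal one.

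Safety is a secondary objective and is analysed descriptively without testing (SAP 5.3), so the abnormality tables do much of the work of showing individual outliers by arm. White cells and neutrophils are of some interest here because the protocol's introduction says that activation of GPR84 "mediates both activation and migration of neutrophils". That raised counts could reflect a drug effect or an infection on treatment is an inference from this biology. Neither document reports or predicts such an effect.

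**Working it through.** The plan states no figure to reproduce. The check applies its written rules to test values.

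**Inputs from the SAP.** Table 8 limits (x 10^9/L): neutrophils, grade 1 below the LLN, then cuts at 1.5, 1.0 and 0.5; platelets, grade 1 below the LLN, then cuts at 75, 50 and 25; WBC decreased, grade 1 below the LLN, then cuts at 3, 2 and 1; WBC increased, grade 3 above 100. Anything meeting no limit is grade 0.

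**Unit check.** 100,000/mm3 x 10^6 mm3/L = 10^11/L = 100 x 10^9/L, so the two unit columns agree.

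**Assumed inputs.** The SAP gives no normal ranges. I assumed WBC 4–11, neutrophils 2–7.5 and platelets 150–400 (x 10^9/L). They set the L/N/H label. No upper limit, whatever its value, changes a grade below, because Table 8 has no upward grade for neutrophils or platelets and only the cut at 100 for WBC.

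| Result (x 10^9/L) | Normal-range class | Table 8 grade | Can be treatment-emergent? |
|---|---|---|---|
| WBC 8 | N | 0 | No |
| WBC 12, 20, 50, 100 | H | 0 | No |
| WBC 100.1 | H | 3 | Yes, if the baseline grade is lower |
| Neutrophils 5 | N | 0 | No |
| Neutrophils 9, 20, 40 | H | 0 | No |
| Platelets 250 | N | 0 | No |
| Platelets 500, 1000 | H | 0 | No |

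The H rows with grade 0 are the gap. They share a shift-table cell with the N rows, and 5.3.2.4 keeps them out of the L/N/H tables.

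**How far the pattern extends.** Across Tables 5 and 8, seven tests are graded both ways: hemoglobin, WBC, lymphocytes, glucose, sodium, potassium and calcium. With eosinophils counted once there are 26 graded tests, so 26 − 7 = 19 are graded in one direction only. If the relative eosinophil count in Table 5 is counted separately, the figures are 27 and 20. For many of these the ungraded direction is of little interest (low ALT, for example). Hemoglobin and lymphocytes are graded upward as well as downward, so the missing upward rows for neutrophils and platelets look like an oversight.

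**Do the means compensate?** As an illustration with assumed values, suppose one of the 40 active-arm subjects in protocol 7.1 rises from 7 to 25 x 10^9/L. The arm mean moves by (25 − 7)/40 = 0.45 x 10^9/L, which is easy to miss. The maximum would show 25, but not how many subjects were high or whether the rise was new.

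**The listing.** 5.3.2.8 requires a result to be treatment-emergent and out of range. Under the graded rule in 5.3.2.6, a grade 0 result fails the first condition. Under the L/H rule in the same section, a new H passes. The text does not say which rule governs a graded test.

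**QRS.** Protocol Appendix 4 sets the limit and SAP 5.3.3.1 includes the parameter, but Table 7 and the abnormality tables in 5.3.3.4 cover only QT, QTcF, PR and HR. A QRS above 120 ms is never classified in those tables, though it may appear in the ECG out-of-range listing.

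**The case against.** The best defence is that little is lost. Protocol 6.5.2 collects the white cell differential as absolute and relative values. The SAP treats the two as separate tests for eosinophils, and the neutrophil row in Table 8 is in cells/mm3. Relative neutrophils are therefore ungraded and keep their L/N/H tables. Descriptive statistics for every test include minimum and maximum (SAP 3.5.2). Out-of-range values are flagged to the investigator, clinically significant ones are recorded as adverse events, and the data monitoring committee sees unblinded safety data. The hematology finding that protocol 2.2.4 does report, raised hematocrit, hemoglobin and red cell count at 200 mg, is covered: high hemoglobin is graded, and the other two are ungraded and so classified by normal range. All of this stands and makes the point minor. It does not repair the tables: relative and absolute counts can diverge, and the adverse event route depends on judgement of significance.

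A second defence reads each Table 8 row as its own test, so that high neutrophils and platelets would count as ungraded. SAP 5.3.2.7 speaks against this, since it treats direction as a level within a test. The WBC gap would remain in any case, because the increase is itself a graded row.

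A reader might infer more than the text supports. It does not follow that normal-range analysis is dropped for every graded test: 5.3.2.2 plans it for glucose and triglycerides, so the two sections conflict. Nor do these results vanish from all output, and their absence from the listing is only one possible reading.

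**Conclusion.** The gap is real and narrow. As written, high absolute neutrophils, high platelets and WBC from the ULN to 100 x 10^9/L are tabulated as grade 0 and never counted as treatment-emergent. With an assumed WBC ULN of 10 to 11 x 10^9/L, the unscored interval spans a factor of about 100/11 = 9.1 to 100/10 = 10. That is the width of the interval, and the documents give no basis for estimating how many subjects would fall in it.

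The conclusion rests on reading a test as the analyte, with direction a level within it, as SAP 5.3.2.7 does. For WBC it holds on either reading. The effect is confined to descriptive safety tables, including the corresponding interim tables in SAP 4.2. No efficacy conclusion changes. The documents do not support the stronger inferences that raised neutrophils are an expected drug effect, or that a marked leukocytosis would go unseen. The QRS omission is a separate, smaller gap of the same kind.

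**What to change.** Before unblinding, amend the SAP as follows.

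- **5.3.2.4:** state that L/N/H is also derived and tabulated, in shift and treatment-emergent tables, for graded tests in any direction that has no grade or whose grading starts beyond the normal limit. Name at least absolute neutrophils high, platelets high and WBC high.
- **5.3.2.8:** state that the abnormality listing uses the same flags, so that a new L or H in such a direction is listed.
- **5.3.2.2 and 5.3.2.4:** reconcile them, so that the normal-range tabulations for glucose and triglycerides are an explicit exception or fall under the new rule.
- **Table 7 and 5.3.3.4 (secondary):** add QRS, using the normal range already in protocol Appendix 4.

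The laboratory position indicators are already in the database and QRS is already an analysed parameter. The cost is SAP wording, a small programming change and a few extra rows. No new data are needed.

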5.3.2.5. Urinalysis Tests with Categorical Results

Results of urinalysis with qualitative results will be tabulated by time point. No toxicity grading or non-graded abnormalities will be derived.

5.3.2.6. Treatment-Emergent Principle

Toxicity Grades

A post-baseline toxicity grade 1, 2, 3 or 4 is defined as treatment-emergent when higher than the toxicity grade of the baseline result. If the baseline result is missing, a post-baseline toxicity grade 1, 2, 3 or 4 will be considered as treatment-emergent.

Non-graded Abnormalities

A post-baseline non-graded abnormality class L or H is defined as treatment-emergent when it differs from the abnormality class of the baseline result. If the baseline result is missing, a post-baseline abnormality L or H will be considered as treatment-emergent.

5.3.2.7. Worst-Case Principle

Toxicity Grading

The worst-case post-baseline toxicity grade 0, 1, 2, 3 or 4 will be determined per subject, per laboratory test (and sense, if below and above) and for each analysis period, using all non-

missing post-baseline records (including unscheduled and follow-up visits, but excluding local lab results).

The worst-case toxicity grade is the highest toxicity grade scored for the laboratory test (in each sense, if below and above).

Non-graded Abnormalities

The following worst-case post-baseline abnormalities L, N, or H will be determined per subject, per laboratory test and for each analysis period, using all non-missing post-baseline records (including unscheduled and follow-up visits, but excluding local lab results):

- L = low: at least one post-baseline result is classified as L.
- N = normal: all post-baseline results are classified as N.
- H = high: at least one post-baseline result is classified as H.

If, for a subject, both L and H are reported, the subject will be counted twice in the table: once with a worst-case L and once with a worst-case H.

5.3.2.8. Presentation of Results

No formal inferential statistics (p-values) will be derived.

Continuous laboratory tests will be summarized by means of descriptive statistics of the actual values and changes from baseline (including 95% CI of the mean change) by laboratory test, treatment group, and analysis window.

Boxplots of the actual values over time and of the mean (+/- SE) change from baseline will be prepared for all laboratory tests.

The analysis of abnormalities will focus on assessments reported during the treatment period. Results reported during the screening or follow-up period will only be listed.

Abnormalities and toxicities grades of the actual values will be presented as shift tables of the worst-case abnormality/toxicity grade versus the baseline abnormality/toxicity grade. The table will be created per laboratory test and treatment group. The results of non-graded abnormalities and toxicities grades will be shown separately.

A frequency table of the number (percent) of subjects with treatment-emergent worst-case abnormalities/toxicity grade per laboratory test and treatment group will be presented. The results of non-graded abnormalities and toxicities grades will be shown separately.

A listing per treatment group, per subject, and per time point of all post-baseline time points scored as treatment-emergent and out-of-normal-range, plus also the baseline reference time point will be provided. In addition, laboratory parameters with insufficient data to be presented in the tables will be listed.

5.3.3. Electrocardiogram

5.3.3.1. Available Data

The following electrocardiogram (ECG) parameters will be analyzed: PR interval, heart rate (HR), RR interval, QRS duration, QT interval, and QTcF interval.

5.3.3.2. Derivation Rules

Derived Parameters

The QTcF values will be used as available in the database.

Handling of ECGs Measured in Triplicate

If ECG is collected in triplicates/duplicates, the following approach will be taken.

The mean of the triplicate/duplicate ECG values will be calculated for each individual ECG parameter, without rounding the result. These calculated means will constitute the analysis values; any derivation (e.g. change from baseline, assignment of abnormalities) and statistic will be based on the mean value of the triplicates/duplicates.

The values of the original members of a triplicate/duplicate will be listed.

5.3.3.3. Abnormalities

The actual analysis values and changes from baseline of the QT and QTcF parameters will be categorized into the abnormality classes as defined in ICH-E14 The Clinical Evaluation of QT/QTc Interval Prolongation and Proarrhythmic Potential for Non-Antiarrhythmic Drugs (Step 4 Version). For PR and HR the categorization as specified in the protocol is used.

Table 7 Abnormalities on ECG Parameters

Parameter	Abnormality	Limits
Abnormalities on actual values		
QT and QTcF (ms)	QT ≤ 450 450 < QT ≤ 480 480 < QT ≤ 500 QT > 500	≤ 450 450 < value ≤ 480 480 < value ≤ 500 > 500
PR (ms)	L N H	< 120 120 ≤ value ≤ 220 > 220
HR (bpm)	L N H	< 50 50 ≤ value ≤ 100 > 100
Abnormalities on change from baseline		

QT and QTcF (ms)	QT change \leq 30	\leq 30
	30 < QT change \leq 60	30 < change \leq 60
	QT change > 60	> 60

Worst-Case Abnormality

The worst-case post-baseline categorized actual analysis value and the worst-case categorized change from baseline will be determined per subject, per parameter, and for each analysis period, using all non-missing post-baseline records (including unscheduled and follow-up visits).

For QT and QTcF, the worst-case categorized actual analysis value is the category corresponding to the highest post-baseline actual value. The worst-case change from baseline is the category corresponding to the largest increase (positive change) from baseline.

For PR and HR, the worst-case post-baseline abnormality L, N or H is determined as follows:

- L = low: at least one post-baseline result is classified as L.
- N = normal: all post-baseline results are classified as N.
- H = high: at least one post-baseline result is classified as H.

If, for a subject, both L and H are reported, the subject will be counted twice in a table: once with a worst-case L and once with a worst-case H.

Treatment-Emergent Abnormalities

For QT and QTcF, an abnormal post-baseline category for actual values is defined as treatment-emergent when the abnormality is worse compared to the abnormality at baseline. When the baseline value is missing, post-baseline abnormalities are considered as treatment-emergent. An abnormal category for change from baseline is always treatment-emergent.

For PR and HR, post-baseline abnormalities L or H are defined as treatment-emergent when they differ from the abnormality class of the baseline result. When the baseline result is missing, post-baseline abnormalities L or H are considered as treatment-emergent.

